### 8.1 Exposure to Trial Medication

Exposure to aripiprazole IMP injections for the safety sample will be summarized using percentage of subjects receiving injections and trial day of each injection from date of randomization by treatment formulation, PK sampling schedule and disease type.

Exposure to oral aripiprazole during the first 1 or 2 weeks after first injection will be summarized using percentage of subjects exposed to oral aripiprazole and daily dose by week in the randomization phase, treatment formulation, disease type and PK sampling schedule.

### 8.2 Adverse Events

All AEs are coded using Medical Dictionary for Regulatory Activities (MedDRA Version 23.0 or later). A treatment-emergent adverse event (TEAE) is defined as an AE which starts after start of first IMP injection or an AE continues from baseline of the treatment phase and was serious, trial drug-related or results in death, discontinuation, interruption or reduction of trial medication. The incidences of the following TEAEs will be reported by MedDRA preferred term, treatment formulation and disease type:

- TEAEs by severity,
- Potentially drug related TEAEs,
- TEAEs with an outcome of death,
- Serious TEAEs,
- Discontinuations due to TEAEs,
- Non-Serious TEAEs.

Protocol 031-201-00181

In addition, sub-group analysis for incidence of TEAEs will be summarized by sex (male and female), race (Caucasian, African American and Other), ethnicity (Hispanic/Latino and Not Hispanic/Not Latino), age (< 45 years old and  $\geq$  45 years old at baseline), BMI ( $\leq$  28 kg/m^2 and > 28 kg/m^2 at baseline), disease type, and PK Robust/Sparse Sampling schedule.

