- Pregnancies are also defined as IREs. Although normal pregnancy is not an AE, it will mandate IMP discontinuation and must be reported on an IRE form to the sponsor. Pregnancy will only be documented on the AE eCRF if there is a complication or abnormality in the newborn.

Protocol 031-201-00181

**Clinical Laboratory Assessment Value Changes:** It is the investigator's responsibility to review the results of all laboratory tests as they become available. This review will be documented by the investigator's dated signature on the laboratory report. For each abnormal laboratory test result, the investigator needs to ascertain if this is an abnormal (ie, clinically relevant) change from baseline for that individual subject. This determination, however, does not necessarily need to be made the first time an abnormal value is observed. The investigator may repeat the laboratory test or request additional tests to verify the results of the original laboratory tests. If this laboratory value is considered clinically relevant by the investigator (eg, subject is symptomatic, requiring corrective treatment or further evaluation), or if the laboratory value leads to discontinuation, or fulfills a seriousness criterion, this is considered an AE.

**Severity:** Adverse events will be graded on a 3-point scale and reported as indicated on the eCRF. The intensity of an AE is defined as follows:

- 1 = Mild:** Discomfort noticed, but no disruption to daily activity.
- 2 = Moderate:** Discomfort sufficient to reduce or affect normal daily activity.
- 3 = Severe:** Inability to work or perform normal daily activity.

**IMP Causality:** Assessment of causal relationship of an AE to the use of IMP:

- Related:** There is a reasonable possibility of a temporal and causal relationship between the IMP and the AE.
- Not Related:** There is no temporal or reasonable relationship between the IMP and the AE.

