## 5.2 Eliciting and Reporting Adverse Events

The investigator will assess subjects for the occurrence of AEs from the time the ICF is signed until the end of the trial. For this trial, information on AEs will be followed for up to 28 days after the last dose of aripiprazole IM depot 400 mg has been administered and 56 days after the last of aripiprazole 2M LAI 960 mg has been administered. To avoid bias in eliciting AEs, subjects should be asked the following nonleading question: "How are you feeling?" All AEs (serious and nonserious) reported by the subject must be recorded on the source documents and eCRFs provided by the sponsor. Serious AE collection is to begin after a subject has signed the ICF.

Use medical terminology in AE reporting. Adverse events should be reported as a single unifying diagnosis whenever possible or, in the absence of a unifying diagnosis, as individual signs or symptoms. Exacerbation or disease progression should be reported as

Protocol 031-201-00181

AEs only if there are unusual or severe clinical features that were not present, not experienced earlier, or not expected based on the course of the condition.

In addition, the sponsor must be notified immediately by telephone, fax, or e-mail of any IREs according to the procedure outlined below in [Section 5.3](#). Special attention should be paid to recording hospitalization and concomitant medications.

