## 7.6 Safety Analysis

### 7.6.1 Adverse Events

All AEs will be coded by system organ class and the Medical Dictionary for Regulatory Activities preferred term. A treatment-emergent adverse event (TEAE) is defined as an AE which starts after the first dose of IMP or an AE that continues from baseline and is serious, IMP-related, or results in death, discontinuation, interruption or reduction of IMP. The incidence of the following events will be summarized by treatment group and by disease type:

- TEAEs
- TEAEs by severity
- TEAEs potentially causally related to the IMP
- TEAEs with an outcome of death
- Serious TEAEs
- TEAEs leading to discontinuation of the IMP

Protocol 031-201-00181

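### The TEAE definition has no worsening criterion, so a pre-injection AE that becomes more severe on treatment can stay out of the AE tables unless it is re-recorded as a new event

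*SAP*

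**What the plan says.** The SAP definition (8.2) has two limbs. Under the first, a TEAE "is defined as an AE which starts after start of first IMP injection". The second covers the case where "an AE continues from baseline of the treatment phase and was serious, trial drug-related or results in death, discontinuation"; given in full, its conditions are that the event "was serious, trial drug-related or results in death, discontinuation, interruption or reduction of trial medication". Protocol 7.6.1 matches it; its second limb is "an AE that continues from baseline and is serious, IMP-related, or results in death, discontinuation, interruption or reduction of IMP".

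AE collection starts well before dosing. Protocol 5.2 has AEs assessed "from the time the ICF is signed until the end of the trial", and screening lasts up to 30 days. Events that predate the first injection will therefore be in the database.

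Severity is recorded. Protocol 5.1 states: "Adverse events will be graded on a 3-point scale and reported as indicated on the eCRF". The grades are mild, moderate and severe.

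The incidence tables in SAP 8.2, including the severity table and the subgroup tables, are confined to TEAEs. The special-interest tables in SAP 8.10 are confined to treatment-emergent events. AEs are one of the primary safety variables in SAP 6.1.

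**The concern.** An AE table in a safety trial should show what got worse on treatment as well as what first appeared. Here a continuing event enters on seriousness, attribution or consequence for dosing, and never on a change of grade.

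Screening events that could worsen are plausible. Under protocol 3.2.2, subjects with no history of tolerating aripiprazole take three 10-mg oral doses on top of their current treatment, at least 14 days before the first injection. Sedation or insomnia present at that stage could intensify on the depot. The plan has no dedicated severity scale for either, so the AE tables are where worsening would be expected to show.

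For a nonserious event that leaves dosing unchanged, inclusion then rests on the investigator's causality call. Protocol 5.1 ties relatedness to a temporal as well as a causal link with IMP. An onset before the first injection makes the temporal part harder to argue, even when the worsening follows the injection.

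**Working it through.** No figure is attached to this point, so the check is of the rule itself.

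**Rule, from SAP 8.2 and protocol 7.6.1.** TEAE = (onset after the first injection) OR (continues from baseline AND at least one of: serious, drug-related, fatal, leads to discontinuation, leads to interruption, leads to reduction).

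**Rule applied to an AE that is mild in screening and severe after the first injection:**

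| Case | How the event is recorded and judged | First limb | Second limb | TEAE? |
|---|---|---|---|---|
| A | One record with a pre-injection start date; none of the six conditions met | No | No | No |
| B | One record with a pre-injection start date; at least one condition met | No | Yes | Yes |
| C | Worsening entered as a new AE with a post-injection start date | Yes | Not needed | Yes |

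The event is lost in case A only. It then appears in no table of SAP 8.2 or 8.10.

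**Do the documents rule out case A by requiring case C?** The places that bear on recording are these:

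- Protocol 5.1, severity: three grades are defined, with no rule for a grade that changes within one event.
- Protocol 5.1, definition of an AE: worsening is mentioned only for medical-history items tied to preplanned procedures.
- Protocol 5.2, exacerbation or disease progression: these are reported as "AEs only if there are unusual or severe clinical features that were not present, not experienced earlier, or not expected" on the course of the condition. Such a report after dosing could enter by the first limb. The wording seems aimed at the underlying illness and does not clearly cover every screening AE.
- Protocol 5.7.1: nonserious AEs are recorded with their current status, ongoing or resolved. Nothing says that a worsened event gets a new record.
- Protocol 3.7.6.3: a clinically significant finding at a post-treatment physical examination becomes an AE if it was absent at the baseline examination. That covers new findings, not worsened ones.

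None of these requires a new record for a worsened AE. Whether a given event falls under A or C is left to the AE form or to site practice.

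**Reach within the safety endpoint.** The EPS scales (SAS, BARS, AIMS), laboratory tests, vital signs, ECG and C-SSRS are analysed by change from baseline, by abnormality criteria or by their own definitions of emergence and worsening. The VAS and the injection-site assessment are tabulated at each injection. None of these depends on the TEAE definition. Only the AE component is affected.

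**Size.** An estimate would need the frequency of AEs ongoing at the first injection, the share that worsen, the share meeting none of the six conditions, and the share not re-recorded. The documents give none of these.

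**The case against.** The strongest reply is that the affected set is narrow and may be empty. The event must start in screening, still be present at the first injection, worsen later, meet none of six conditions and stay in its original record. A severe event is one that prevents work or normal daily activity, so some would meet another condition. An aripiprazole-type event that began with the oral tolerability doses and worsened on the depot is a natural candidate for a related judgement, which already counts. Restlessness is also captured by change in BARS. Protocol 5.1 defers to the eCRF for how severity is reported, and the eCRF is not among the documents, so the recording convention may exist there.

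Much of this stands. It limits the reach of the gap but does not close it: neither document states the convention, and the rule as written excludes case A.

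A reader might infer more than the texts support:

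- *That an unrelated judgement alone removes a worsened event.* It does not. All six conditions must fail.
- *That the overall TEAE rate is biased downward.* This is not shown. The second limb also admits continuing events that are serious or related without any worsening, so the net direction for the overall rate is open.
- *That the arms are biased against each other.* The trial is open-label, and interruption or reduction can arise only at later injections: 4 − 1 = 3 in the 960 mg arm and 8 − 1 = 7 in the 400 mg arm. These are possible mechanisms only. The definition is identical in both arms, screening events arise before Day 1 randomization, and nothing in the documents shows a direction or size.

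**Conclusion.** The point holds in a limited form. Neither TEAE definition has a worsening criterion. A continuing AE that increases in severity after the first injection and meets none of the six conditions is not a TEAE, and it is absent from the TEAE, severity and special-interest tables unless the worsening is re-recorded as a new AE. On-treatment worsening can thus be undercounted in the AE component of the primary safety endpoint.

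This rests on one assumption that the documents neither confirm nor exclude: that at least some worsening is kept in the original record. The size of the undercount cannot be estimated, and a difference between arms is not shown. The change is still worth making, because the gap lies in a stated classification rule and is cheap to close.

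**What to change.** Add a third limb to the definition in SAP 8.2 and protocol 7.6.1, for example: *or an AE present at baseline that increases in severity after the first IMP injection*. State that such an event is tabulated at its highest post-injection severity.

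A recording rule would do the same job without changing the definition: worsening of an ongoing AE after the first injection is entered as a new AE with its own start date, and so qualifies under the first limb. Either route is enough. The one chosen should be written down.

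The cost is one clause or one recording instruction and a slightly higher TEAE count. The AE form must capture the change in severity and show that it came after the first injection; this should be checked before the first route is relied on.

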### 8.3 Vital Signs

Vital signs include body temperature in supine position, systolic/diastolic blood pressure in supine and standing position and heart rate. Potential clinically relevant vital sign abnormalities will be listed, the criteria for which are provided in [Appendix 1](#).

Incidences of clinically relevant vital signs abnormalities based on observations during scheduled visits and unscheduled post-baseline visits will be tabulated by treatment formulation and disease type. In addition, vital sign parameters and changes from baseline will be summarized by scheduled visit, treatment formulation and disease type.

If vital sign assessments are repeated for the same trial visit, the last repeat values will be used for production of summary tables. This is accomplished by sorting patient data by visit date and visit time (if applicable) within the same trial visit.

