**Table 3.7.3-2 Sparse Sampling Schedule Trial Days and Activities**

| Days 36, 43, and 50 ± 2 days (outpatient, subjects receiving aripiprazole 2M LAI 960 mg)   |  |
|---|--|
| 
 
• Document birth control methods.
 
• Record concomitant medications and review for prohibited or restricted medications.
 
• Record adjustment of current oral antipsychotic, mood stabilizer, or antidepressant therapy.
 
• Assess and record AEs.
 
• Take vital signs (systolic and diastolic blood pressure, heart rate, and body temperature).
 
• Administer the Since Last Visit version of the C-SSRS.
 
• Draw a PK blood sample between 8 AM and 2 PM.
 
  |  |
| Day 57 ± 2 days (outpatient, all subjects)   |  |
| 
Predose:
 
 
• Document birth control methods.
 
• Record concomitant medications and review for prohibited or restricted medications.
 
• Record adjustment of current oral antipsychotic, mood stabilizer, or antidepressant therapy.
 
• Assess and record AEs.
 
• Perform a urine pregnancy test (FOCBP only).
 
• Measure weight.
 
• Take vital signs (systolic and diastolic blood pressure, heart rate, and body temperature).
 
• Administer a 12-lead safety ECG in triplicate (5 minutes apart).
 
• Administer the Since Last Visit version of the C-SSRS.
 
• Assess EPS (SAS, AIMS, and BARS).
 
• Administer the PANSS (schizophrenia subjects only).
 
• Administer CGI-S scale, CGI-I scale, and SWN-S (all subjects).
 
• Administer the MADRS, YMRS, and CGI-BP (bipolar subjects only).
 
• Draw a PK blood sample (within 2 hours prior to dosing).
 
• Assessment and confirmation by the investigator that the injection site is appropriate 30 minutes prior to IMP injection.
 
• Have subjects complete a VAS of the level of perceived pain at the injection site completed approximately 30 minutes prior to IMP injection.
 
• Administer IMP.
 
 |  |
| 
Postdose:
 
 
• Have subjects complete a VAS of the level of perceived pain at the injection site approximately 1 hour (± 15 minutes) postdose.
 
• Assessment of the injection site by the investigator completed approximately 1 hour (± 15 minutes) postdose.
 
  |  |

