**Days 176, 183, and 190  $\pm$  2 days (outpatient, subjects receiving aripiprazole 2M LAI 960 mg)**

- Document birth control methods.
- Record concomitant medications and review for prohibited or restricted medications.
- Record adjustment of current oral antipsychotic, mood stabilizer, or antidepressant therapy.
- Assess and record AEs.
- Take vital signs (systolic and diastolic blood pressure, heart rate, and body temperature).
- Administer the Since Last Visit version of the C-SSRS.

Protocol 031-201-00181

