**Table 3.7.3-2 Sparse Sampling Schedule Trial Days and Activities**

|  |  |
|--|--|
| • Draw a PK blood sample between 8 AM and 2 PM.  | Day 197 ± 2 days (outpatient, all subjects) |
| • Document birth control methods.  |  |
| • Record concomitant medications and review for prohibited or restricted medications.  |  |
| • Record adjustment of current oral antipsychotic, mood stabilizer, or antidepressant therapy.                                       |  |
| • Assess and record AEs.   |  |
| • Perform a urine pregnancy test (FOCBP only).   |  |
| • Measure weight and calculate BMI.  |  |
| • Take vital signs (systolic and diastolic blood pressure, heart rate, and body temperature).  |  |
| • Administer the Since Last Visit version of the C-SSRS.   |  |
| • Assess EPS (SAS, AIMS, and BARS).  |  |
| • Administer the PANSS (schizophrenia subjects only).  |  |
| • Administer CGI-S scale and SWN-S (all subjects).   |  |
| • Administer the MADRS, YMRS, and CGI-BP (bipolar subjects only).  |  |
| Subjects who receive aripiprazole 2M LAI 960 mg only:   |  |
| • Draw a PK blood sample between 8 AM and 2 PM.  |  |
| Subjects who receive aripiprazole IM depot 400 mg only:   |  |
| Predose:  |  |
| • Assessment and confirmation by the investigator that the injection site is appropriate 30 minutes prior to IMP injection.          |  |
| • Have subjects complete a VAS of the level of perceived pain at the injection site approximately 30 minutes prior to IMP injection. |  |
| • Draw a PK blood sample within 2 hours prior to dosing.   |  |
| • Administer IMP.  |  |
| Postdose:   |  |
| • Have subjects complete a VAS of the level of perceived pain at the injection site 1 hour ( $\pm$ 15 minutes) postdose.             |  |
| • Assessment of the injection site by the investigator completed approximately 1-hour ( $\pm$ 15 minutes) postdose.                  |  |
| • Draw a PK blood sample 4, 8, and 12 hours postdose.  |  |
| Days 204, 211, and 218 ± 2 days (outpatient, all subjects)  |  |
| • Document birth control methods.  |  |
| • Record prior and concomitant medications and review for prohibited or restricted medications.                                      |  |
| • Record adjustment of current oral antipsychotic, mood stabilizer, or antidepressant therapy.                                       |  |

Protocol 031-201-00181

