## 5.2 Trial Week Windows

The actual assessment date is mapped into the trial week. The definition of trial weeks for primary PK variables are described in [Table 5.2-1](#) and the definitions of trial weeks for efficacy scales and safety scales such as Extrapyramidal Symptoms (EPS) rating scales are included in [Table 5.2-2](#) and [Table 5.2-3](#). Trial days are derived from the formula: Trial Day = Date of assessment - Date of 1st IMP injection + 1. Based on the number of trial days, subjects are mapped to the corresponding trial week. For safety and efficacy variables, only the last observation within the same mapped trial week is used for imputing data on the following trial weeks in the derived last observation carried forward (LOCF) dataset. In addition, only last observations within the same mapped weeks are reported in the summary tables by trial week.

Table 5.2-1 Time Window for Trial Weeks for Primary PK Variables C28 and C56		
Scheduled Visit (Day)	Mapped Week (Trial Week)	Week Window (Trial Day Range ± 2 days)
197	28 (28 days after the 7th injection of 400 mg Abilify Maintena)	195-199
225	32 (28 days after the 8th injection of 400 mg Abilify Maintena or 56 days after the 4 th injection of 960 mg aripiprazole 2M LAI)	223-227

Table 5.2-2 Time Window for Mapping Trial Week for Efficacy Variables		
Scheduled Visit (Day)	Mapped Week (Trial Week)	Week Window (Trial Day Range)
1	Baseline	≤1 (before first IMP)
29	4	2-43
57	8	44-85
113	16	86-141
169	24	142-183
197	28	184-211
225	32	212-239

Protocol 031-201-00181

Table 5.2-3 Time Window for Mapping Trial Week for Safety Variables		
Scheduled Visit (Day)	Mapped Week (Trial Week)	Week Window (Trial Day Range)
1	Baseline	≤1 (before first IMP)
8	1	2-11
15	2	12-18
22	3	19-25
29	4	26-43
57	8	44-71
85	12	72-99
113	16	100-127
141	20	128-155
169	24	156-183
197	28	184-211
225	32	212-239

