## 8 Safety Analyses

Safety assessments including adverse events (AEs), vital signs, ECGs, clinical laboratory monitoring (serum chemistry, hematology, urinalysis), physical examinations, EPS, VAS scores for pain perception, investigator's assessment of most recent injection site, and suicidality via the C-SSRS will be summarized for the safety sample by treatment formulation and disease type in addition to all treated subjects.

In summarizing the incidence of clinically relevant abnormalities in clinical laboratory results, vital sign measurements and ECG measurements, a subject must have had an evaluation that meets the specified criteria. Incidence rate will be calculated as the number of subjects having at least 1 abnormality in the treatment phase divided by the number of subjects in the safety sample.

Safety data collected during in-clinic visits and virtual visits are summarized together.

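### Vital-sign checks differ by arm (960 mg v 400 mg: sparse 20 v 14; robust 32 v 35; sparse under the COVID-19 rule 4 v 8), so the any-visit incidence of abnormalities is not comparable between arms

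*SAP*

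**What the plan says.** SAP 8 defines the incidence rate as the "number of subjects having at least 1 abnormality in the treatment phase divided by the number of subjects in the safety sample". SAP 8.3 applies it to vital signs: "Incidences of clinically relevant vital signs abnormalities based on observations during scheduled visits and unscheduled post-baseline visits will be tabulated by treatment formulation". That table is further split by disease type. The sampling schedule is not a dimension of it, although the SAP does split disposition (7.1), demographics (7.2), exposure (8.1) and the adverse-event subgroups (8.2) by it.

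The visit schedule differs by arm. In the sparse schedule (Protocol Table 3.7.3-2) one block of visits is headed "Days 36, 43, and 50 ± 2 days (outpatient, subjects receiving aripiprazole 2M LAI 960 mg". The block for "Days 176, 183, and 190" is likewise for 960 mg subjects only. The closing block is shared: "Days 204, 211, and 218 ± 2 days (outpatient, all subjects". Vital signs are listed at every one of these visits. In the robust schedule (Table 3.7.3-3), Days 36, 43 and 50 are for 960 mg only, and Days 198, 199, 201, 206, 209 and 214 are for 400 mg only.

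SAP 7.1 places Day 225 inside the treatment phase for both arms. SAP 7.5 says that during COVID-19 restrictions sparse subjects attend the clinic on dosing days and Day 225, with remote safety assessments in between. Vital signs are not among the examples it gives of remote assessments.

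**The concern.** The chance that a subject has at least one flagged value rises with the number of times the subject is measured. If the arms are measured a different number of times, the tabulated percentages differ even when the risk per measurement is the same. Safety and tolerability is the first-listed primary objective, the trial is open-label, and this is the SAP's by-arm summary of flagged vital signs. As scheduled, laboratory tests, ECGs and weight fall on the same days in both arms, so vital signs are the exception. Because the table pools the sampling schedules, a reader can neither see nor remove the imbalance.

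**Working it through.** The documents state no number of vital-sign checks, so there is no plan figure to reproduce.

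**Counts** (Protocol Tables 3.7-1, 3.7-2, 3.7.3-2 and 3.7.3-3; Day 1 is predose and so is baseline)

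- Sparse, both arms: Days 8, 15, 22, 29, 57, 85, 113, 141, 169, 197, 204, 211, 218, 225 = 14. Adding Days 36, 43, 50, 176, 183, 190 for 960 mg gives 20 v 14.
- Robust, both arms: Days 2, 3, 5, 8, 10, 13, 15, 18, 22, 29, 57, 85, 113, 141, 169, 170, 171, 173, 176, 178, 181, 183, 186, 190, 197, 204, 211, 218, 225 = 29. Adding 3 for 960 mg and 6 for 400 mg gives 32 v 35.
- Sparse under SAP 7.5, clinic visits only: Days 57, 113, 169, 225 (4) v Days 29, 57, 85, 113, 141, 169, 197, 225 (8).

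**Mean checks per subject.** Protocol 3.1 plans 91 sparse and 38 robust subjects per arm.

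- 960 mg: (91×20 + 38×32)/129 = 3036/129 = 23.5
- 400 mg: (91×14 + 38×35)/129 = 2604/129 = 20.2
- Ratio 1.17, against 20/14 = 1.43 for sparse alone.

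**Incidence with no true difference.** For k independent checks, each with probability p of a flagged value, P(at least one) = 1 − (1 − p)^k. The value of p is an assumption; the documents give none. At p = 1%:

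| | 960 mg | 400 mg | Ratio |
|---|---|---|---|
| Sparse | 18.2% | 13.1% | 1.39 |
| Robust | 27.5% | 29.7% | 0.93 |
| Pooled, as the SAP tabulates | 20.9% | 18.0% | 1.16 |
| Sparse, all under SAP 7.5 | 3.9% | 7.7% | 0.51 |
| Pooled, all sparse under SAP 7.5 | 10.9% | 14.2% | 0.77 |

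Pooled rows weight the strata 91:38. For p from 0.25% to 5%, the planned pooled ratio runs from 1.17 to 1.14.

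**Correlated checks.** A beta-binomial with a = p(1/ρ − 1) and b = (1 − p)(1/ρ − 1) gives P = 1 − Γ(b+k)Γ(a+b)/[Γ(b)Γ(a+b+k)]. At p = 1%:

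| ρ | Sparse ratio | Pooled ratio |
|---|---|---|
| 0.1 | 1.23 | 1.12 |
| 0.3 | 1.15 | 1.08 |
| 0.5 | 1.10 | 1.06 |

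**Where the direction turns.** Per 129 subjects per arm, the planned excess of checks for 960 mg is 3036 − 2604 = 432. With all sparse follow-up under SAP 7.5 it is (91×4 + 38×32) − (91×8 + 38×35) = 1580 − 2058 = −478. The excess is gone when 432/(432 + 478) = 432/910, about 47%, of sparse follow-up is under that rule.

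**Effect of matching days.** On common days the planned counts are 14 v 14 and 29 v 29, so the null ratio is 1.00. Under SAP 7.5 the 14 sparse days still leave 4 v 8, because Days 29, 85, 141 and 197 are 400 mg dosing days only. Days 57, 113, 169 and 225 give 4 v 4 under either regime.

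**The case against.** The best defence has four parts.

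- The table is descriptive and no between-arm safety test is planned. That is correct, and it limits the consequence. It does not make the two percentages comparable.
- The effect may be very small. Appendix 1 requires a change from one fixed baseline, which links a subject's checks, so independence is implausible. At p = 2% and ρ = 0.5 the pooled figures are 7.2% v 6.8%, about half a subject in 129. That stands as the low end of the range.
- Part of the remedy is already planned. Protocol 7.4.1 foresees the incidence of vital-sign abnormalities by visit, and SAP 8.3 lists every abnormality and summarises changes by scheduled visit. However, the incidence table in SAP 8.3 has no visit dimension, and none of these displays gives a per-subject incidence on matched days.
- Replacing the all-visit table would lose information. Protocol 1.3 reports median tmax of 25.1 and 41.0 days after single 780 mg and 1200 mg doses, so Days 36 to 50 may lie near the test product's peak. Unscheduled readings would go too. This stands, and is why the matched-day table should be added to the all-visit table and not replace it.

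A reader might also infer that the windows in SAP Table 5.2-3 distort the by-visit vital-sign tables, since the 960 mg-only days have no row there. The documents do not establish that: SAP 8.3 summarises vital signs by scheduled visit.

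**Conclusion.** The any-visit incidence of vital-sign abnormalities is not comparable between arms, because the number of checks differs by arm and by sampling schedule and nothing in SAP 8 or 8.3 allows for it. On the planned schedule the pooled null ratio is about 1.16 at p = 1% with independent checks (20.9% v 18.0%), and 1.06 to 1.12 with correlation of 0.1 to 0.5.

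A reader might infer from the sparse count of 20 v 14 that the schedule alone inflates the 960 mg incidence, by a ratio near 1.39. The documents do not support that. The table pools the schedules, the robust schedule runs the other way, and SAP 7.5 turns the sparse count into 4 v 8, with a pooled ratio down to about 0.77 if all sparse follow-up is affected. How much is affected is not stated, so the direction is unknown in advance.

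The figures rest on an assumed p that is equal in both arms, on Day 225 lying in the treatment phase, and on vital signs not being taken at remote visits (the SAP's list is only of examples). Robust counts are held at plan. Dropout and unscheduled visits are not modelled. If the treatment phase were read as ending at the last dose, the sparse count would be 12 v 10. The weight criterion in Appendix 1 is unaffected as scheduled, since weight is measured on the same days in both arms.

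**What to change.** Keep the all-visit incidence table and the listing of every abnormality. Add to SAP 8.3:

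1. A by-arm incidence table, split by sampling schedule, restricted to days scheduled in both arms: the 14 sparse days and 29 robust days listed in the working.
2. A sparse version on Days 57, 113, 169 and 225, which both arms attend in clinic under either regime.
3. The number of vital-sign assessments per subject, by arm.
4. A sentence saying that between-arm statements rest on the matched-day table.

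The cost is SAP wording and a few tables. The matched-day tables leave out arm-specific and unscheduled readings, but those stay in the all-visit table and the listing, so no safety data are lost.
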